### 7.1.3 Secondary Efficacy Endpoints

All secondary efficacy endpoints will compare GNX and PBO at the end of the 17-week DB treatment phase relative to the 6-week prospective baseline phase. If any endpoint value at baseline is zero, then any percentage changes from baseline for that endpoint will be missing.

All secondary analyses will be done primarily in the ITT population and secondarily in the PP population.

#### 7.1.3.1 Change from baseline in the Percentage of Seizure-Free Days Based on the Primary Seizure Types

The percentages of seizure-free days will be based on the primary seizure types. Post-baseline percentage of seizure-free days will be calculated as the number of days in the 17-week DB treatment phase with zero seizures divided by the number of days with seizure data in the phase, multiplied by 100. The baseline percentage of seizure-free days will be calculated as the number of days in the 6-week baseline phase with zero seizures divided by the number of days with seizure data in the baseline phase, multiplied by 100.

The baseline and post-baseline values and the arithmetic changes from baseline will be summarized using descriptive statistics.

#### 7.1.3.2 Percentage of Subjects Experiencing $\geq 50\%$ Reduction from Baseline in 28-day Seizure Frequency Based on the Primary Seizure Types

The number and percentage of subjects experiencing a reduction (improvement) of at least 50% from baseline in the 28-day seizure frequency of the primary seizure types will be summarized. In addition, a cumulative responder curve figure will be provided, in which the X-axis represents amount of improvement in increments of 5%, and the Y-axis represents the percentage of subjects improving by at least the amount on the X-axis. The treatment groups will be presented separately within the figure.

### 7.1.3.3 Change in Seizure Intensity/Duration

The CGI-CSID is from the 7-point Caregiver Global Impression of Change in Seizure Intensity/Duration instrument. The scores range from 1=very much improved and 7=very much worse. The number and percentage of subjects with each score will be summarized.

### 7.1.3.4 Behavioral/Neuropsychiatric Endpoints

The CGICA, CGI-C, and the CGI-I are all 7-point scales, and the number and percentage of subjects with each score will be summarized. The scores range from 1=very much improved and 7=very much worse. (The CGI-I is completed by both parent/caregiver/LAR and clinician.)

[REDACTED]

[REDACTED]

[REDACTED]

[REDACTED]

[REDACTED]

- [REDACTED]
- [REDACTED]
- [REDACTED]

[REDACTED]

[REDACTED]

[REDACTED]

[REDACTED]

[Redacted]

[Redacted]

[Redacted]

[Redacted]

[Redacted]

- [Redacted]

- [Redacted]

[Redacted]

[Redacted]

[Redacted]

[Redacted]

[Redacted]

[Redacted]

[Redacted]

[REDACTED]

- [REDACTED]
- [REDACTED]

[REDACTED]

- [REDACTED]
- [REDACTED]
- [REDACTED]
- [REDACTED]
- [REDACTED]
- [REDACTED]
- [REDACTED]
- [REDACTED]

[REDACTED]

[REDACTED]

[REDACTED]

[REDACTED]

[REDACTED]

[REDACTED]

[REDACTED]

### **7.1.5 Subgroup Analyses**

Two subgroup summarizations of the primary efficacy parameter are planned. The first one is by Allo\_S levels [(low ( $\leq 2.5$  ng/mL), middle ( $> 2.5$  ng/mL and  $< 6.0$  ng/mL) or high ( $\geq 6.0$  ng/mL)], and since there may be a potentially greater treatment effect among subjects with low levels the subgroup with low levels will be analyzed as a sensitivity analysis; see Section 7.1.8 for additional details. The second subgroup is by gender.

### **7.1.6 Analysis of Weeks 5 and 9**

In order to explore the time course of GNX on non-seizure endpoints, the analyses of those endpoints will be repeated using the data from the scheduled Week 5 and Week 9 visits.

### **7.1.7 Protections for Multiplicity**

There is a single primary efficacy endpoint, and formal hypothesis testing will not be performed for the other endpoints. Hence no protections for multiplicity are needed.

### **7.1.8 Sensitivity Analyses**

Three sensitivity analyses of the primary efficacy endpoint of change in 28-day frequency of the primary seizure types will be performed:

Intermittent (random/sporadic) missing data during the 17-week DB phase and any missing data during the baseline phase will be assumed missing completely at random and the collected data will be used to calculate the 28-day seizure frequencies. For early drug termination prior to the end of the 17-week DB phase, caregivers will be instructed to continue to provide daily seizure records until the end of the 17-week DB phase (hence further preventing missingness).

In the first sensitivity analysis, the following imputation approach will be used for the primary outcome measure when a subject stops recording measurements permanently (anticipated to be

minimal in occurrence) prior to the end of the 17-week DB phase: for those missing days, the corresponding median PBO data will be imputed (irrespective of treatment arm) as follows:

- Partition the subjects in the PBO arm into quartiles, where the quartile equals  $\text{Floor}[\text{Rank} \cdot 4 / (n + 1)]$ , where  $\text{Floor}[\cdot]$  is the integer floor function, Rank is the rank of the 28-day seizure frequency in the PBO arm based on all available PBO measurements during the 6-week baseline phase (tied scores receive tied ranks), and n is the number of subjects in the PBO arm.
- Assign each subject for whom imputation is needed into the quartile that covers the 28-day seizure frequency based on that subject's available measurements during the 6-week baseline phase. If a frequency is lower than the lower bound of the lowest quartile (which could happen only in the GNX arm), then assign that subject to the lowest frequency quartile; likewise if a frequency is higher than the upper bound of the highest quartile, then assign that subject to the highest frequency quartile. If a frequency falls between two quartiles (which, again, could happen only in the GNX arm), then based on the distances between the frequency and the upper and lower bounds of the lower and higher quartiles, respectively, assign the subject to the closer quartile (in case of a tie, assign to the lower quartile).
- Within each quartile, compute the median 28-day seizure frequency in the PBO arm based on all available PBO measurements during the 17-week DB treatment phase. Label that 'X', and define 'A' to be  $X/28$ , (i.e., the daily average on placebo during the 17-week DB phase).
- For any days (whether they be on the PBO or GNX arm) with missing counts due to a subject stopping recording measurements permanently, impute 'A' from the corresponding quartile on that day.

The second sensitivity analysis will explore the possibility that subjects who stop recording their seizure counts tend to have higher seizure counts than the other subjects. The imputation method described in the 3rd and 4th bullets above, except that quartiles are not used, will be modified to use the median of the 5 highest counts (equivalent to the 3rd highest count) among all the PBO subjects with data.

The third sensitivity analysis is to examine the effect of GNX compared to PBO among subjects with low Allo-S levels. The open-label phase 2 study 1042-0900 enrolled 30 subjects who were treated for up to six months. In these subjects with various pediatric epilepsies, including 11 with PCDH19 genetic epilepsy and 7 with CDKL5 Deficiency Disorder, Allo-S levels and 28-day seizure rates were assessed. A GNX responder was specified, by post-hoc definition, as having at least a 25% reduction in 28-day seizure rate. In the PCDH19 cohort, responders (n=6) and non-responders (n=5) had plasma Allo-S concentrations of  $501 \pm 430$  pg mL and  $9,829 \pm 6,638$  pg mL, respectively (mean  $\pm$  SD). When performing a retrospective separation of the PCDH19 cohort according to their Allo-S levels, the 7 subjects with Allo-S levels below 2,500 pg mL had a 53.9% reduction in seizure rates while the 4 subjects with Allo-S levels above 2,500 pg mL had a 247% increase.

All 7 of the subjects with CDKL5 Deficiency Disorder in the 1042-0900 study had low Allo-S levels (below 1000 pg/mL), and their median 28-day seizure reduction was 31%.

The PCDH19 cohort results were based on only 11 subjects and were from an uncontrolled study. Even if low Allo-S levels are indeed associated with increased efficacy of GNX relative to PBO among patients with PCDH19 seizures, this effect modification by baseline Allo-S levels will not necessarily hold among subjects with CDKL5 seizures; it does nevertheless suggest that among patients suffering with CDKL5 seizures the benefit of GNX compared to PBO could be greater in patients with low Allo-S levels. As a result, most important sensitivity analysis for the effect of GNX on the primary efficacy endpoint of change in 28-day frequency of the primary seizure types will be in those subjects with low Allo-S levels at baseline. Based upon insights from the Study 1042-0900 clinical trial data, subjects in this trial will be considered to have low Allo-S levels if they have a baseline Allo-S level of less than or equal to 2500 pg/mL (Pinna Lab method).

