9. DATA MANAGEMENT AND STATISTICAL METHODS

9.1. Data Collection

The investigator's authorized site personnel must enter the information required by the protocol on the eCRF. A study monitor will visit each site in accordance with the monitoring plan and review the eCRF data against the source data for completeness and accuracy. Discrepancies between source data and data entered on the eCRF will be addressed by qualified site personnel. When a data discrepancy warrants correction, the correction will be made by authorized site personnel. Data collection procedures will be discussed with the site at the site initiation visit and/or at the investigator's meeting. Once a subject is screened, it is expected that site personnel will complete the eCRF entry within approximately 7 business days of the subject's visit.

The subject's parent/caregiver/LAR must enter the information required by the protocol in the eDiary. A study monitor will review all seizure diary entries in accordance with the monitoring plan for completeness and accuracy. Discrepancies will be addressed by the subjects' parent/caregiver/LAR and qualified site personnel. When a data discrepancy warrants correction, the correction will be made by the subjects' parent/caregiver/LAR and authorized site personnel. Data collection procedures will be discussed with the site at the site initiation visit and/or at the investigator's meeting. Once the subject's parent/caregiver/LAR signs informed consent, it is expected that all eDiary entries will be made daily and no longer than 48 hours after each day.

Telephone Follow-up visits are allowed to be conducted via secure email per institutional policy if granted by individual sites IRB/EC.

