## 2.5 Handling of Missing Data

Missing data will not be replaced except as noted. Missing efficacy data will be imputed in a sensitivity analysis as described in [Section 7.1.7](#).

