### 7.1.1 Handling of Missing Data

The primary analysis will use all available data. Careful educating and monitoring of the study sites will attempt to limit the amount of missing data to nearly zero, but despite these efforts, some missing data may still arise. Thus a sensitivity analysis, in which the missing data will be replaced, will be performed on the primary efficacy endpoint; see [Section 7.1.8](#).

When an item from a secondary or efficacy endpoint is missing, then so will any subscales or totals that include it.

When subjects prematurely discontinue from the study they are asked to complete the non-seizure assessments at the Taper Visit. For analysis purposes, their data from the Taper Visit will be reassigned to the first visit at which the assessment is scheduled subsequent to the discontinuation and the scheduled day is within 32 days of the Taper visit. For example if a subject completed Visit 3 and then prematurely discontinued and completed assessments at the Taper Visit on Study Day 100, then the Taper visit would be reassigned to Visit 5 (Week 17) for analysis purposes since Visit 5 is scheduled for Study Day 120, 20 days after the assessments were actually completed. (Although the first visit after Visit 3 is Visit 4 (Week 9), that visit is scheduled on Study Day 64, which is not within 32 days of Study Day 100.) But if the Taper Visit assessments were completed on Study Day 28 then the Taper visit would not be reassigned to a regular study visit since Study Day 28 is not within the 32-day window of any scheduled visit. Taper Visit assessments that are not reassigned will not be included in the tabulations but will be included in the data listings.

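### Sensitivity analyses 1 and 2 impute only after a permanent diary stop, so a long double-blind gap that ends is analysed from the collected days alone

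*SAP*

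**What the plan says.** SAP 7.1.8 describes two kinds of missing double-blind diary data. The first is handled by assumption: "Intermittent (random/sporadic) missing data during the 17-week DB phase and any missing data during the baseline phase will be assumed missing completely at random", with the 28-day frequencies calculated from what was collected. The second is imputed. In sensitivity analysis 1, days "with missing counts due to a subject stopping recording measurements permanently" receive the daily placebo value for the matching baseline quartile.

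Sensitivity analysis 2 "will explore the possibility that subjects who stop recording their seizure counts tend to have higher seizure counts than the other subjects". It reuses the last two steps of analysis 1 without the quartiles and changes the imputed value to the third highest placebo count. The trigger is the same permanent stop. Analysis 3 is the low Allo-S comparison and involves no imputation: "The third sensitivity analysis is to examine the effect of GNX compared to PBO among subjects with low Allo-S levels".

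Elsewhere the default is to leave gaps alone. SAP 2.5 states: "Missing data will not be replaced except as noted". SAP 7.1.1 adds: "The primary analysis will use all available data". SAP 7.1.2 divides total seizures by the number of days with seizure data, so a missing day leaves both numerator and denominator. The first supportive interim analysis in SAP 10 borrows the analysis 1 procedure, again for permanent stoppers only. No section gives a maximum length for an intermittent gap.

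**The concern.** Whether a gap is stress-tested depends on whether the subject ever records again, not on how many days are missing or why. Two subjects can lose almost the same stretch of diary. The one who never returns is imputed, and the one who makes a single late entry is not.

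Analyses 1 and 2 are there to show whether absent diary days could explain the result. If long gaps coincide with worsening, these analyses would stay silent about them and could look more reassuring than they should. Long gaps are possible. Subjects who stop drug are asked to keep the diary going, and Protocol 4.5.1 warns of more or worse seizures after abrupt discontinuation. Under Protocol 9.1 "it is expected that all eDiary entries will be made daily and no longer than 48 hours after each day", so a longer lapse may not be filled in afterwards. The documents do not say how often this will happen.

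**Working it through.** **The plan's own figures, for scale.** SAP 1.3.2: SD 44.5, 50 per arm, difference 30, one-sided 0.025.
- Standard error = 44.5 × √(2/50) = 8.90.
- Power = Φ(30/8.90 − 1.96) = Φ(1.41) = 0.921, against the stated 92%.
- Threshold = 1.96 × 8.90 = 17.4, against the stated 17.5.

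These reproduce and are not in dispute.

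**One subject, 60-day gap.** SAP 7.1 starts the phase the day after first treatment and SAP 7.1.1 places Visit 5 on Study Day 120, so Days 2 to 119 give 118 diary days. The following are assumed: baseline 40 per 28 days, rate 20 on recorded days, rate 40 during the gap, placebo quartile median 40.
- Gap on Days 50–109, recording resumes on Days 110–119: 58 days recorded. The primary analysis and sensitivity analyses 1 and 2 all give 20/40 − 1 = **−50%**.
- True change: (58×20 + 60×40)/118/40 − 1 = **−24.6%**.
- Same subject, but no return after Day 49: 48 days recorded, 70 imputed. Sensitivity analysis 1 gives (48×20 + 70×40)/118/40 − 1 = **−20.3%**.

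At −50% the subject also counts as a responder on the ≥50% reduction endpoint; at −24.6% it would not.

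**Effect of gap length.** Same assumptions, with the gap imputed at the baseline rate instead of ignored:

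| Gap (days) | As written | Gap imputed as in analysis 1 |
|---|---|---|
| 14 | −50% | (104×0.5 + 14)/118 − 1 = −44.1% |
| 28 | −50% | (90×0.5 + 28)/118 − 1 = −38.1% |
| 55 | −50% | (63×0.5 + 55)/118 − 1 = −26.7% |

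For the 55-day gap, losing the single last-day entry makes it a permanent stop of 56 days, and analysis 1 then gives (62×0.5 + 56)/118 − 1 = −26.3%. With the placebo median at 0.9 to 1.1 times baseline, that figure runs from −31.0% to −21.5%.

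**Does the per-protocol analysis catch these subjects?** Protocol 6.6 and 7.4.1 exclude subjects below 80% compliance at two consecutive visits. Take clinic visits on Days 36 (from Week 5), 64 and 120 and the between-visit formula of SAP 7.1.
- Gap on Days 50–109: 14/28 = 50%, then 10/56 = 18%. Excluded, if the rule covers diary compliance.
- Gap on Days 64–118: 28/28 = 100%, then 1/56 = 2%. Only one interval fails, so the subject stays in if only clinic visits count, with 63 recorded days (9 weeks, above the 5-week minimum).

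**Trial level.** Suppose a share f of ganaxolone subjects have such gaps and no placebo subject does. The mean difference is then overstated by f × (50 − 38.1) for 28 days, or f × (50 − 26.7) for 55 days.
- f = 2%: 0.2 to 0.5 points.
- f = 10%: 1.2 to 2.3 points.
- f = 20%: 2.4 to 4.7 points.

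**The case against.** A reader might infer that the SAP declares every gap that ends to be completely at random, in every analysis. The documents do not support that. The assumption in 7.1.8 is worded for random or sporadic gaps, and a 60-day block is not obviously one of those. Such a block is left unclassified and gets available-day handling by default. The per-protocol analysis may also exclude some of these subjects, including the 60-day example if the 80% rule means diary compliance. The rule does not say whether it means diary or drug compliance, or whether telephone contacts count as visits. Even so, exclusion is not imputation, and it does not test the ITT result.

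Gaps are not invisible either. SAP 7.1 summarises diary compliance up to the last available entry, with the percentage at least 80% compliant; the 60-day example would show 58/118 = 49%. But this summary alters no analysis and reports neither the number nor the length of gaps.

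Safeguards exist. The diary is reviewed at Day 3 and Weeks 1–5, 9, 11, 13 and 17, entries are monitored for completeness, and a paper calendar is available with sponsor approval. The 48-hour rule is an expectation, not a stated lockout. That gaps would follow worsening is conjecture. All of this stands, and it makes long gaps less likely.

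The effect is probably small as well. A rank-sum test on about 100 subjects moves little when one subject shifts from −50% to −25%, and gaps on placebo would offset those on ganaxolone.

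**Conclusion.** The gap in the rule is real: 7.1.8 sets no limit on an intermittent gap, and one late entry removes a long double-blind gap from both imputation analyses. For one subject under the assumed rates the difference is about 25 percentage points. For the trial it is roughly 0.2 to 4.7 points over the assumed range. The upper end needs one ganaxolone subject in five with a 55-day gap at the baseline rate and no such gaps on placebo. The documents give no count of such subjects, and SAP 7.1.1 aims for almost no missing data.

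It would go too far to conclude that the primary result is likely to be biased, or that the primary analysis should change. What is supported is narrower: the imputation analyses do not cover one foreseeable pattern of missing data, and covering it is cheap.

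**What to change.** Before unblinding, amend SAP 7.1.8 as follows.

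1. State a maximum length for an intermittent double-blind gap. The documents supply no value; 14 or 28 consecutive days would each be a stated choice. In the illustration, a gap at the cut-off that is left unimputed hides about 6 points for one subject at 14 days and about 12 at 28.
2. In sensitivity analysis 1, apply the placebo-quartile imputation to every longer double-blind gap, in either arm, whether or not recording resumes.
3. Tabulate the number and length of such gaps by arm.

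Leave the primary analysis and the permanent-stop trigger of sensitivity analysis 2 unchanged. Analysis 2 uses an extreme value that would override a returning subject's own data. With that value assumed at 2 to 5 times baseline, one imputed week alone would move −50% to (111×0.5 + 7×2)/118 − 1 = −41%, or (111×0.5 + 7×5)/118 − 1 = −23%.

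The cost is a sentence or two in the SAP, a small programming change and one table. The downside is somewhat more imputed days and a cut-off that has to be chosen. The cross-reference in SAP 2.5 can be corrected at the same time: it points to 7.1.7 for the imputation, which is in 7.1.8.

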### 1.3.2 Sample Size and Statistical Power Considerations

Based on data from the 7 patients in Study 1042-0900 evaluating GNX in CDKL5 patients, the standard deviation for the percent change in 28-day seizure frequency for seizure types tonic (sustained motor activity  $\geq 3$  seconds), tonic-clonic, atonic/drop, epileptic spasms, or clonic (generalized or unilateral) is estimated to be 44.5. Therefore, when the percent change in 28-day seizure frequency on GNX minus that on PBO truly is 30%, then a trial with 100 subjects randomized in a 1:1 manner will have 92% power to detect this effect when using an ANOVA that preserves a (one-sided) 2.5% false positive error rate. If the true difference in the percent changes is 35%, then the study will have 97.5% power.

The threshold for achieving statistical significance at the final analysis when 100 subjects have completed their 17-week DB treatment phase would be an estimate of the difference that is approximately 17.5%. (The actual analysis will use a Wilcoxon rank-sum test, which has approximately the same power as the ANOVA.)

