### 7.1 Double-Blind Phase

All efficacy analyses will be conducted in the ITT population. A supportive analysis of the primary and secondary efficacy endpoints also will be conducted in the PP population.

The estimand that is most clinically relevant as well as estimable in a manner that protects the integrity of randomization is the outcome measure (e.g., the percent change in 28-day seizure frequency), where ALL randomized subjects would be included in this analysis throughout the study period. Hence, all available data will be used, even if they were collected after the subject stopped taking study medication, regardless of whether the subject took rescue medication. [Section 7.1.1](#) details the handling of missing data.

For the analyses of seizures, the baseline phase consists of 6 weeks before the first day of treatment and the DB phase starts the day following the first day of DB treatment until the final visit for subjects who do not enter the OLE and up to the day before the first dose of OLE treatment for those who do. The first day of treatment is not in either phase since the seizures could occur both before and after the first treatment.

Tests of significance between the 2 treatment groups will be performed for the primary endpoint with a 2-sided significance level of 0.05.

Seizure diary compliance for the baseline and the post-baseline DB phase intervals will be calculated as:

$100 \times (\text{Number of Days with Available Seizure Diary}) / (\text{Last Available Seizure Diary Date} - \text{First Day of the Phase} + 1)$ .

Seizure diary compliance between visits will be calculated as:

$100 \times (\text{Number of days with available seizure data between visits}) / \text{Number of days between visits}$ , with the days between visits defined as the day of the prior visit up to the day before the current visit.

The compliances will be summarized with descriptive statistics and the percentage of subjects at least 80% compliant.

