### 7.1.2 Primary Efficacy Endpoint

The primary efficacy endpoint is the percent change from baseline in 28-day primary seizure frequency during the 17-week DB treatment phase. Primary seizure types include bilateral tonic, generalized tonic-clonic, atonic/drop, bilateral clonic, or focal to bilateral tonic-clonic seizures. Post-baseline 28-day seizure frequency will be calculated as the total number of seizures in the 17-week DB treatment phase divided by the number of days with seizure data in the phase, multiplied by 28. Baseline 28-day seizure frequency will be calculated as the total number of seizures in the baseline phase divided by the number of days with seizure data in the phase,

multiplied by 28. The calculation for percent change from baseline in 28-day seizure frequency will be done as follows for each subject:

$$\left( \frac{[(\text{Post-baseline 28-day seizure frequency}) - (\text{Baseline 28-day seizure frequency})]}{(\text{Baseline 28-day seizure frequency})} \right) \times 100\%$$

The baseline and post-baseline values and the changes and percent changes from baseline in 28-day seizure frequency will be summarized using descriptive statistics.

The difference between the treatment groups in the percent changes from baseline will be tested for statistical significance. Since the percent differences are anticipated to display skewness and/or outliers, the tests will be performed using the Wilcoxon Rank-Sum statistic.

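### Phase-level diary compliance stops counting at the last diary entry, so a subject who records daily and then stops for good scores 100%; separately, and optionally, sensitivity analysis 1 could scale its imputed rate to the subject's own baseline

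*SAP*

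**What the plan says.** **Diary compliance (SAP 7.1).** There are two formulas. The phase-level one divides the days with diary data by the days from the start of the phase to the "Last Available Seizure Diary Date", inclusive. The between-visit one divides by all days from the previous visit to the day before the current visit. Both are summarised descriptively and as "the percentage of subjects at least 80% compliant".

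The same section defines the phases for seizure analyses. Baseline is the six weeks before first treatment. The double-blind phase runs from the day after first treatment to the day before the first open-label (OLE) dose, or to the final visit for subjects who do not enter the OLE.

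**Imputation (SAP 7.1.8).** Analyses 1 and 2 fill days "with missing counts due to a subject stopping recording measurements permanently". Analysis 1 splits the placebo arm into quartiles of baseline frequency and places each stopper, from either arm, in a quartile by own baseline. The next step reads: "Within each quartile, compute the median 28-day seizure frequency in the PBO arm based on all available PBO measurements". That median, X, divided by 28 fills every missing day. At the top end, "likewise if a frequency is higher than the upper bound of the highest quartile, then assign that subject to the highest frequency quartile". Analysis 2 drops the quartiles and uses the third-highest placebo value, in order to "explore the possibility that subjects who stop recording their seizure counts tend to have higher seizure counts than the other subjects".

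**Endpoint (SAP 7.1.2).** The seizure count is "divided by the number of days with seizure data in the phase, multiplied by 28", and the result is expressed as percent change from the subject's own baseline.

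**The concern.** SAP 7.1.1 relies on site education and monitoring to keep missing diary data close to none. Whole-phase diary compliance is where a reader would check whether that worked. With this denominator, days after a permanent stop drop out of the calculation, and those are exactly the days that analyses 1 and 2 have to impute. A report could show compliance near 100% beside a sensitivity analysis that fills many weeks.

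The second issue is one of scale. The endpoint is a ratio to own baseline, but the imputed quantity is a count rate common to a whole quartile. Two stoppers in the same quartile with different baselines receive the same daily count and so different imputed percent changes, for no reason connected with their course.

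**Working it through.** **Compliance (exact)**

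Inputs: SAP 7.1.1 puts Visit 4 on Study Day 64 and Visit 5 on Study Day 120. By the same rule Visit 3 (Week 5) is Day 36. For a subject whose first OLE dose is on Day 120, the double-blind phase is Day 2 to 119 = 118 days. For a non-entrant seen on Day 120 it is Day 2 to 120 = 119 days.

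| Case | Phase-level formula | Between-visit formula | Share of phase |
|---|---|---|---|
| Diary Day 2–49, then none; visits kept; enters OLE | 48/48 = 100% | Day 36–63: 14/28 = 50%; Day 64–119: 0/56 = 0% | 48/118 = 40.7% |
| Diary Day 2–22, then none; no later visit | 21/21 = 100% | no interval closes after the stop | 21/119 = 17.6% |

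In general, daily recording for D days followed by a permanent stop gives D/D = 100% for every D.

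**Imputation: algebra**

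Let B be the subject's baseline 28-day frequency, R the frequency while recording, f the fraction of phase days missing, and r the quartile's median placebo ratio of post-baseline to baseline frequency.

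- SAP rule: percent change = 100 × {[(1 − f)R + fX]/B − 1}.
- Scaled rule (fill with r × B instead of X): 100 × {[(1 − f)R + f·r·B]/B − 1}.
- Difference: 100 × f × (X/B − r).

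For a subject with no change while recording (R = B), the SAP rule gives f(X/B − 1) = f(r − 1) + f(X/B − r). The first term is the placebo trend that the analysis intends to apply. The second is the extra noise. It depends on position within the quartile (through X/B) and on stop time (through f).

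Illustration with assumed X = 250 and r = 1, stopping after 28 of 118 days (f = 90/118 = 0.763):

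- B = 500: 0.763 × (0.50 − 1) = −38%
- B = 320: 0.763 × (0.78 − 1) = −17%
- B = 180: 0.763 × (1.39 − 1) = +30%

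Stopping after 90 days instead (f = 28/118 = 0.237), B = 500 gives 0.237 × (−0.5) = −12%. The scaled rule gives 0 in all four cases.

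**Imputation: effect on the analysis**

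The documents give no baseline distribution and no stopping rate, and they state no figure for this analysis. The one design input used is the SD of the percent change, which "is estimated to be 44.5" (SAP 1.3.2). It reproduces the stated power: SE = 44.5 × √(2/50) = 8.9, and 30/8.9 − 1.96 = 1.41, which gives 92%.

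Simulation assumptions: 50 per arm, log-normal baseline (log-SD 1.0 or 1.2), placebo SD of percent change 44.0 to 44.6, stop after 28 of 118 days, two-sided Wilcoxon test at 0.05, 4000 trials per setting.

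| Result | SAP rule | Scaled rule |
|---|---|---|
| Mean distance of a stopper's rank from its full-data rank (of 100) | 23 to 26 | 17 to 19 |
| Rejection under the null | 4.3 to 5.4% | 4.4 to 5.7% |
| Power near 80%, 2 stoppers per arm | 79.4 to 80.4% | 80.1 to 81.3% |
| Power near 80%, 5 stoppers per arm | 74.3 to 76.8% | 77.1 to 79.6% |

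Setting by setting, the loss near 80% power is 0.7 to 1.3 points with 2 stoppers per arm and 2.3 to 2.8 points with 5. Near 97% power it is 0 to 0.8 points. With stop times spread over the phase, the rank distances fall to about 15 to 17 against 10 to 13. Across these variations the loss with 2 stoppers per arm is about 0 to 1.4 points.

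A further set of runs used a true 30% reduction, stop days spread over days 14 to 105, and the overall placebo ratio for scaling. Power was 97.0% against 97.1% with 5% stoppers, 96.5% against 96.9% with 10%, and 95.1% against 96.2% with 20%. With unequal stopping (10 or 20% on ganaxolone, 4% on placebo), at random or among the highest baselines, null rejection under the SAP rule was 3.9 to 4.4%.

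**The case against.** **On compliance.** A denominator ending at the last entry is a defensible measure of adherence while recording, and SAP 7.1.8 does treat sporadic gaps separately from permanent stops. Between-visit compliance exposes the first case above. Caregivers are told to keep the diary after drug is stopped, the diary is reviewed at each contact, and SAP 3.1 counts and lists withdrawals. All of this stands, and it makes the gap minor. It does not close it: between-visit compliance needs a later visit, disposition counts subjects rather than diary days lost, and no listed summary gives the share of the phase recorded.

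It is also fair to say that the final visit may mean an early-termination visit, since Protocol 7.2.3 lists the same procedures for that case. Counting to Day 120 is therefore a rule to be added, not one that SAP 7.1 already contains. It would mix attrition with adherence, which is a reason to report both figures.

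**On imputation.** Quartile matching already removes much of the mismatch, and filling days with counts fits an endpoint built from counts over days. Most of a stopper's rank displacement also remains under the scaled rule. These points stand, so this part is only a refinement.

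**Stronger readings that the documents do not support.**

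- A reader might infer that stoppers are let into the per-protocol set. SAP 2.2.2 requires at least 5 weeks of post-baseline seizure data, and the 80% exclusion in Protocol 6.6 and 7.4.1 works by consecutive visits. Neither uses the phase-level figure.
- A reader might infer that analysis 1 favours ganaxolone. The rule is the same in both arms and no type I inflation appeared.
- A reader might infer that trial decisions are at risk. The primary analysis imputes nothing (SAP 7.1.1), and at the interims this imputation is informational only (SAP 10).
- A reader might fault analysis 2 on the same ground. It is a deliberate extreme and can stay.

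**Conclusion.** The compliance point holds exactly and needs no assumption beyond the SAP's own formula and visit days. A permanent stop after perfect recording always scores 100%, even when as little as 18 to 41% of the phase is recorded, as in the two cases shown. The consequence is confined to a descriptive figure that would misstate how complete the primary-endpoint diary is.

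The imputation point is real but small. It concerns a supportive analysis, adds noise and not demonstrated bias, and matters little with the few stoppers that the SAP expects. The sizes rest on the assumed baseline distribution, stop times and stopping rates, and the illustrated percent changes are off only relative to an assumed course without change. Overall this is a low-priority improvement: the first part is worth making, the second is optional.

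**What to change.** **Compliance.** Divide by the planned days of the phase:

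- Baseline: 42 days.
- Double-blind, OLE entrants: Study Day 2 to the day before the first OLE dose.
- Double-blind, non-entrants who attend Visit 5: Study Day 2 to that visit.
- Added rule for subjects who leave without Visit 5: count to its scheduled day (Study Day 120, 119 days).

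The present figure can be kept beside it, labelled as adherence while recording. The cost is SAP wording and minor programming, with no new data. Reported compliance may look lower and will include attrition, which a footnote should say.

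**Imputation (optional).** Keep the quartiles, but fill each missing day with the subject's own baseline daily rate times the quartile's median placebo ratio of post-baseline to baseline 28-day frequency. This keeps the placebo-based assumption, puts it on the endpoint's scale, and needs only a few lines of programming. Analysis 2 needs no change.
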